4.1. General Considerations

Statistical analysis of this study will be the responsibility of Eli Lilly and Company (Lilly) or its designee. All tests of treatment effects will be conducted at a 2-sided alpha level of 0.05, unless otherwise stated, and all CIs will be given at a 2-sided 95% level, unless otherwise stated. Statistical analysis will be performed using SAS software (SAS, version 9.1.2 or higher).

Continuous variables will be summarized using descriptive statistics (that is, number of participants, mean, median, standard deviation, minimum, and maximum). Categorical variables will be summarized by frequency and its corresponding percentage.

Any change to the data analysis methods described in the protocol will require an amendment ONLY if it changes a principal feature of the protocol. Any other change to the data analysis methods described in the protocol, and the justification for making the change, will be described in the CSR. Additional exploratory analyses of the data will be conducted as deemed appropriate.

4.1.1. Definitions

Definitions of efficacy and safety analysis variables are listed in respective sections of the SAP. Other variables are listed below alphabetically:

- baseline: baseline is defined as the last value recorded for a variable prior to the patient receiving the first dose of selpercatinib
- common conventions:
 - 1 pound = 0.454 kg
 - 1 inch = 2.54 cm
 - 1 year = 365.25 days. Year is calculated as (days/365.25) and will be rounded up to 1 significant digit for purposes of presentation
 - 1 month = 30.4375 days. Month is calculated as (days/30.4375) and will be rounded up to 1 significant digit for purposes of presentation
 - dates, time, and date/time fields will be displayed in data listings in ISO 8601 formats
 - change from baseline = test value at Visit X – baseline value, and
 - percentage change from baseline = $100 \times (\text{test value at Visit X} - \text{baseline value}) / \text{baseline value}$
- Study day: Study day is calculated as assessment date/event date – first dose date + 1 day if the assessment is done on or after the first dose day. If the assessment is done prior to the first dose day, study day will be calculated as assessment date/event – first dose date.

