Highly selective tyrosine kinase inhibitors (TKIs) that inhibit RET are lacking, but several multikinase inhibitors (MKIs) with some degree of anti-RET activity are already in the clinic, and two MKIs, cabozantinib and vandetanib, have received regulatory approval for advanced MTC (irrespective of the presence or absence of a *RET* mutation), with tumor response rates of 28% and 45% and progression-free survival (PFS) improvements (over placebo) of 7.2 and 11.2 months, respectively (Wells, Robinson et al. 2012, Elisei, Schlumberger et al. 2013). The different degree of benefit observed in each study was most likely due to the eligibility requirement for recent tumor progression in the cabozantinib study but not the vandetanib study. In subset analyses of both studies, patients whose tumors harbored *RET* activating mutations derived greater benefit than *RET* mutation-negative patients (Wells, Robinson et al. 2012, Sherman, Clary et al. 2016). Preliminary data suggests similar, moderate activity for MKIs with anti-RET activity in *RET* fusion-positive lung cancer, with response rates of 16-53% (depending on the specific MKI and patient population), but PFS of only 3.6–7.3 months, in several ongoing Phase 2 studies (Drilon, Rekhtman et al. 2016, Lee 2016, Velcheti 2016, Yoh, Seto et al. 2016).

The efficacy of these MKIs is ultimately limited by incomplete inhibition of RET in tumors in patients, significant toxicity from stronger inhibition of other targets (e.g., KDR/VEGFR2, EGFR, MET), and poor pharmacokinetics (PK) (i.e., significant drug accumulation and long half-life contributing to toxicity but not efficacy) in patients. As a result, the majority of patients treated with these agents experience significant toxicities requiring dose interruptions, reductions, and/or treatment cessation.

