4.3.3. Duration of Response

DOR will be calculated for patients with CR or PR as their best overall response. For such patients, DOR is defined as the number of months from the start date of CR or PR (whichever response status is observed first) and subsequently confirmed, to the first date that recurrent or disease progression is objectively documented. If a patient dies (irrespective of cause) without documentation of recurrent or PD beforehand, then the date of death will be used to denote the response end date.

DOR will be right censored for patients who meet one or more of the following conditions:

- subsequent anticancer therapy or cancer-related surgery in the absence of documented disease progression
- died or experienced documented disease progression after missing 2 or more consecutively scheduled disease assessment visits
- alive and without documented disease progression on or before the data cutoff date, and
- discontinue treatment and loss to follow up.

If a patient meets more than one of these conditions, then the scenario that occurs first will be used for the analysis. The event or censoring date will be determined based on the conventions listed in [Table JZLA.4.1](#).

Table JZLA.4.1. DOR Censoring Scheme

Situation	Date of Event or Censoring	Outcome
Death or disease progression between planned disease assessments	Date of death or first disease assessment showing disease progression, whichever occurs first	Event
Subsequent anticancer treatment started before disease progression or death (without disease progression beforehand)	Date of last evaluable disease assessment prior to start of subsequent anticancer treatment	Censored
Death or disease progression after missing 2 or more consecutively scheduled disease assessments	Date of last evaluable disease assessment visit without documentation of disease progression before the first missed visit	Censored
Alive and without disease progression	Date of last evaluable disease assessment	Censored
Discontinue treatment and loss to follow up	Date of last evaluable disease assessment	Censored

Abbreviation: DOR = duration of response.

The patient's overall response status as of the date cutoff date will be summarized by tabulating the number and percentage of patients with confirmed CR or PR as follows:

- response continuing
- subsequent anticancer therapy/cancer-related surgery without documented disease progression beforehand
- discontinued treatment and loss to follow up

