4.3.9. Progression-Free Survival

PFS is defined as the number of months elapsed between the date of the first dose of selpercatinib and the earliest date of documented disease progression or death (whatever the cause). Unless specified otherwise, the analytical methods described in Section 4.3.3 for DOR will be used for PFS. PFS will be calculated as follows:

$$\text{PFS (months)} = (\text{Event or Censoring Date} - \text{First Dose Date} + 1) / 30.4375$$

PFS will be right censored for patients who met one or more of the following conditions:

- no postbaseline disease assessments unless death occurred prior to the first planned assessment (in which case death will be considered a PFS event)
- subsequent anticancer therapy or cancer-related surgery in the absence of documented disease progression
- died or documented disease progression after missing 2 or more consecutively scheduled disease assessment visits
- alive and without documented disease progression on or before the data cutoff date, and
- discontinue treatment and loss to follow up.

If a patient meets more than one of these conditions, then the scenario that occurs first will be used for analysis. The event or censoring date will be determined based on the conventions listed in [Table JZLA.4.2](#).

Table JZLA.4.2. PFS Censoring Scheme

Situation	Date of Event or Censoring	Outcome
Death before first planned disease assessment	Date of death	Event
Death or disease progression between planned disease assessments	Date of death or first disease assessment showing disease progression, whichever occurs first	Event
No postbaseline disease assessments	Date of first dose of selpercatinib	Censored
Subsequent anticancer treatment started before disease progression or death (without disease progression beforehand)	Date of last evaluable disease assessment prior to start of subsequent anticancer treatment	Censored
Death or disease progression after missing 2 or more consecutively scheduled disease assessments	Date of last evaluable disease assessment visit without documentation of disease progression before the first missed visit	Censored
Alive and without disease progression	Date of last evaluable disease assessment	Censored
Discontinue treatment and loss to follow up	Date of last evaluable disease assessment	Censored

Abbreviation: PFS = progression-free survival.

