4.3.10. Overall Survival

OS is defined as the number of months elapsed between the date of the first dose of selpercatinib and the date of death (whatever the cause). Patients who are alive or lost to follow-up as of the data cutoff date will be right-censored. The censoring date will be determined from the date the

patient was last known to be alive. Based on these considerations, OS will be calculated as follows:

$$\text{OS (months)} = (\text{Death or Censoring Date} - \text{First Dose Date} + 1) / 30.4375$$

The duration of OS will be summarized descriptively using the Kaplan-Meier method with the 95% CI about the median calculated using Greenwood's formula. Median follow-up for OS will be estimated according to the reverse Kaplan-Meier estimate of potential follow-up (Schemper and Smith 1996).

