5.1.2. Cancer History

The following variables will be summarized across patients to describe the types of cancers:

- primary cancer diagnosis (standardized term)
- stage of disease at initial diagnosis (I–IV)
- time since initial diagnosis (years)
- metastatic disease at enrollment (yes, no)
- time since initial diagnosis of metastatic disease (years)

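### SAP 4.1.1 rounds displayed months and years up to one significant digit, where one decimal place was probably meant

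*SAP*

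**What the plan says.** The rule stands among the common conventions in SAP 4.1.1 (Definitions). For months: "Month is calculated as (days/30.4375) and will be rounded up to 1 significant digit for purposes of presentation". For years: "Year is calculated as (days/365.25) and will be rounded up to 1 significant digit for purposes of presentation".

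The time-to-event endpoints are in months. In SAP 4.3.3, "DOR is defined as the number of months from the start date of CR or PR"; in 4.3.9, "PFS is defined as the number of months elapsed between the date of the first dose of selpercatinib and the earliest date"; in 4.3.10, "OS is defined as the number of months elapsed between the date of the first dose of selpercatinib and the date of death". Time to response (4.3.6), time to best response (4.3.7) and time on treatment (4.5.6.1) are also in months. The formulas for TTR, TTBR, PFS, OS and time on treatment divide by 30.4375, the divisor in 4.1.1. Time since initial diagnosis and time since diagnosis of metastatic disease (5.1.2) are in years. None of these sections states a number of decimals or a rounding direction of its own.

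**The concern.** The number of significant digits counts from the leading digit, so the precision it gives depends on the size of the value. Between 1 and 10 months one significant digit means whole months. Between 10 and 100 months it means tens of months. The SAP also gives a direction, upward, which shifts displayed values one way instead of leaving rounding error centred on zero.

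The study has no comparator, and its time-to-event results are descriptive Kaplan-Meier summaries, so the displayed medians are what a reader takes away. Durations above 10 months are to be expected: the data cutoff in SAP section 3 waits until responding *RET* fusion-positive thyroid patients have 12 months of follow-up from response onset, or have progressed. This SAP version governs the final clinical study report. A programmer who follows 4.1.1 would produce uninformative duration tables. One who silently corrects it would depart from the written plan.

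**Working it through.** The documents give no worked duration, so there is no figure of the plan's own to reproduce. The check applies the stated rule to example values.

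**Inputs**
- Months = days / 30.4375; years = days / 365.25 (SAP 4.1.1).
- Display rule: upward, one significant digit (SAP 4.1.1).
- Example values: 7.2 and 11.2 months appear in Protocol 1.1, where they describe other drugs ("progression-free survival (PFS) improvements (over placebo) of 7.2 and 11.2 months, respectively"). The values 22.0 months and 5.2 years are chosen for illustration and are not in the documents. None is a result of this trial.

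**Formula.** For a value x, let u = 10^floor(log10 x). The literal rule shows ceil(x/u) × u.

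**Steps**
1. 341 days / 30.4375 = 11.203 months. Here u = 10, x/u = 1.1203, the ceiling is 2, and the display is 20.
2. 670 days / 30.4375 = 22.012 months. Here u = 10, x/u = 2.2012, the ceiling is 3, and the display is 30.

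| Value | Upward, 1 significant digit (as written) | Nearest, 1 significant digit | Nearest, 1 decimal place |
|---|---|---|---|
| 7.2 months | 8 | 7 | 7.2 |
| 11.2 months | 20 | 10 | 11.2 |
| 22.0 months | 30 | 20 | 22.0 |
| 5.2 years | 6 | 5 | 5.2 |

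**Size on these examples, rule as written**
- 7.2 months: (8 − 7.2)/7.2 = 11%
- 11.2 months: (20 − 11.2)/11.2 = 79%
- 22.0 months: (30 − 22.0)/22.0 = 36%

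These percentages depend on the values chosen.

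**Ranges that collapse to one display, in whole days**
- 305 to 608 days (10.02 to 19.98 months) are all shown as 20.
- 609 to 913 days (20.01 to 30.00 months) are all shown as 30.

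The distortion is largest just above 10 months: at 305 days it is (20 − 10.02)/10.02, just under 100%.

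**Where the effect is small or absent.** Values between 1 and 10 months move to the next whole month. Values under 1 month move only to the next tenth: 22 days / 30.4375 = 0.72 is shown as 0.8. Values already at one significant digit do not move.

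**Direction at one decimal place.** If the precision were corrected but upward rounding kept, 341 days would show as 11.3 and 670 days as 22.1, against 11.2 and 22.0 with nearest rounding. If the discarded part is spread evenly between 0 and 0.1, the average upward shift is 0.05 month, or 0.05 × 30.4375 = 1.5 days.

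**The case against.** **The literal reading is implausible.** No statistician would intend every duration between 10 and 20 months to appear as 20, and any competent programmer would use one decimal place. This is probably true, and it is why the point is minor. It does not make the sentence right: neither upward nor nearest rounding to one significant digit gives a usable table, and the rule appears twice.

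**The rule may not reach the endpoints.** SAP 4.1.1 opens by saying that efficacy and safety variables are defined in their own sections and that other variables follow. The endpoint formulas contain no rounding step. This is a fair reading of the lead sentence. But the rule is listed as a common convention, most of the endpoint formulas repeat its divisor, and no endpoint section replaces it. If it did not apply, the SAP would have no display rule for its main durations.

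**Nothing in the analysis changes.** This stands. The text limits rounding to presentation, so event and censoring dates, Kaplan-Meier estimates and confidence intervals are computed from unrounded values. ORR and its exact binomial interval are not durations.

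**Stronger readings a reader might infer.** One is that rounding up flatters the drug throughout. It does not: longer DOR, PFS and OS look better, longer times to response and to best response look worse, and time since diagnosis has no favourable direction. Another is that every displayed duration would be wrong, which fails for values already at one significant digit. A third is that results of this trial have been inflated. The documents contain no results displayed under this rule and give no ground for saying so.

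**Conclusion.** The rule is wrong as written and should be corrected; the point is minor. Followed literally, it shows durations above 10 and up to 20 months as 20, and those above 20 and up to 30 months as 30. Displayed DOR, PFS, OS and time on treatment would be overstated, and displayed TTR and TTBR lengthened.

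This rests on two readings. The first is that the common conventions govern the endpoint displays, which the SAP supports because no other section sets a rule. The second is that the direction word means upward; if it means only ordinary rounding, the illustrative 11.2 and 22.0 become 10 and 20, and the defect remains. That one decimal place was intended is an inference from what a usable table needs, not something the SAP states. The point does not extend to bias in the estimates or to the primary endpoint.

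**What to change.** In both the month bullet and the year bullet of SAP 4.1.1, replace the direction and precision with *rounded to the nearest one decimal place (half up)*, and keep the existing limit to presentation. With that wording 341 days displays as 11.2 months and 670 days as 22.0 months. State the direction as well as the precision, so that the small upward shift at one decimal place does not persist.

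The cost is two phrases in one section. Design, data collection, derivations and analyses are unchanged.

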4.1.2. Handling of Dropouts or Missing Data

4.1.2.1. Missing Data

For data summarized over time by visit, no imputations will be performed on missing data. All analyses will be based on observed data only. The effective sample sizes at each assessment visit

will be based on the total number of patients with nonmissing data for the parameter of interest at that visit.

Missing or partially missing dates for initial disease diagnosis will be imputed. If the month and year of the diagnosis are provided but the day is missing, the missing day is imputed as 15. If only the year is provided, then the missing month and day are imputed as July 1 for the calculation.

4.1.2.2. Unscheduled Visits

In general, for by-visit summaries, data will be presented based on the visit number and corresponding visit name (that is, name of planned clinical encounter). Visit windowing will not be used for handling unscheduled visits. Instead, all unscheduled visits will be assigned a visit name of “Unscheduled.” Such visits will be included in all by-visit summaries and data listing and will contribute to the derivation of best- or worst-case values when required.

The visit number for unscheduled visits will be assigned by adding 0.01 to the visit number of the previously scheduled visit to facilitate chronological sorting. As an illustration, if an unscheduled visit occurs after Study Date 1, where the visit number is “1,” the unscheduled visit will have visit number of “1.01.”

4.2. Participant Dispositions

A detailed description of participant disposition will be provided, according to Consolidated Standards of Reporting Trials publishing requirements, including a summary of the number and percentage of participants entered the study, enrolled in the study, and treated, as well as number and percentage of participants completing the study or discontinuing prior to study completion (overall and by reason for discontinuation).

The disposition of patients will be summarized by tabulating the number and percentage of patients as of a data cutoff date:

- treatment disposition
 - starting dose of selpercatinib and frequency of administration
 - continuing to receive selpercatinib, and
 - permanently discontinued selpercatinib and the primary reason
- study disposition
 - patients who discontinued from study and the primary reason, and
 - time on study.

Patients with PD may be allowed to continue study drug if, in the opinion of the investigator, the patient is deriving clinical benefit from continuing study treatment, and continuation of treatment is approved by the sponsor. The number and percentage of such patients continuing to receive study drug after the documentation of disease progression will be presented.

4.3. Primary Endpoint Analysis

The primary endpoint is ORR based on RECIST version 1.1 by IRC.

4.3.1. Definition of Endpoint

BOR for each patient (CR, PR, SD, PD, or inevaluable) occurring between the first dose of selpercatinib and the date of documented disease progression or the date of subsequent anticancer therapy or cancer-related surgery will be determined based on the RECIST 1.1. All objective responses will be confirmed by a second scan at least 28 days after the initial response.

BOR will be summarized descriptively to show the number and percentage of patients in each response category. Waterfall plots may be used to depict graphically the maximum decrease from baseline in the sum of the diameters of target lesions.

The estimate of ORR will be calculated based on the maximum likelihood estimator (that is, crude proportion of patients with BOR of CR or PR). The estimate of the ORR will be accompanied by 2-sided 95% exact binomial CI.

4.3.2. ORR by Investigator Assessment

Best overall response for each patient based on the RECIST 1.1 by investigator assessment will be analyzed as a secondary endpoint analysis. ORR by investigator will be analyzed in the same manner as ORR by IRC.

To evaluate agreement between IRC and investigator assessments, 2×2 contingency table will be prepared. Correspondence rate and its 2-sided 95% exact binomial CI will be estimated.

4.3.3. Duration of Response

DOR will be calculated for patients with CR or PR as their best overall response. For such patients, DOR is defined as the number of months from the start date of CR or PR (whichever response status is observed first) and subsequently confirmed, to the first date that recurrent or disease progression is objectively documented. If a patient dies (irrespective of cause) without documentation of recurrent or PD beforehand, then the date of death will be used to denote the response end date.

DOR will be right censored for patients who meet one or more of the following conditions:

- subsequent anticancer therapy or cancer-related surgery in the absence of documented disease progression
- died or experienced documented disease progression after missing 2 or more consecutively scheduled disease assessment visits
- alive and without documented disease progression on or before the data cutoff date, and
- discontinue treatment and loss to follow up.

If a patient meets more than one of these conditions, then the scenario that occurs first will be used for the analysis. The event or censoring date will be determined based on the conventions listed in [Table JZLA.4.1](#).

Table JZLA.4.1. DOR Censoring Scheme

Situation	Date of Event or Censoring	Outcome
Death or disease progression between planned disease assessments	Date of death or first disease assessment showing disease progression, whichever occurs first	Event
Subsequent anticancer treatment started before disease progression or death (without disease progression beforehand)	Date of last evaluable disease assessment prior to start of subsequent anticancer treatment	Censored
Death or disease progression after missing 2 or more consecutively scheduled disease assessments	Date of last evaluable disease assessment visit without documentation of disease progression before the first missed visit	Censored
Alive and without disease progression	Date of last evaluable disease assessment	Censored
Discontinue treatment and loss to follow up	Date of last evaluable disease assessment	Censored

Abbreviation: DOR = duration of response.

The patient's overall response status as of the date cutoff date will be summarized by tabulating the number and percentage of patients with confirmed CR or PR as follows:

- response continuing
- subsequent anticancer therapy/cancer-related surgery without documented disease progression beforehand
- discontinued treatment and loss to follow up
- documented disease progression, and
- died (for patients who did not have documented disease progression beforehand).

DOR will be summarized descriptively using the Kaplan-Meier method (Kaplan and Meier 1958). The Kaplan-Meier estimate with 95% CI calculated using Brookmeyer and Crowley method will be provided for the median. The event-free rate with the 95% CI calculated using Greenwood's formula will be provided for selected time points. Median follow-up for DOR will be estimated according to the reverse Kaplan-Meier estimate of potential follow-up (Schemper and Smith 1996).

